Optimization of glucose levels in pregnancy can reduce the risk of several adverse outcomes, which include miscarriage, congenital birth defects, macrosomia, intrauterine fetal demise, and neonatal morbidity ². Traditionally in pregnancy, patients with diabetes would monitor blood glucose levels four times daily: fasting and then 1- or 2-hours postprandial. However, more recently, continuous glucose monitoring (CGM) has become more popular and readily available. In a cohort of patients using CGM, Bartal et al. found that the proportion of the time glucose levels were within what is considered acceptable range, referred to as time in range was associated with neonatal outcomes ³. Specifically, patients whose time in range was below 70% had worse neonatal outcomes than those with time in range at or above 70%.

We hypothesize that post-prandial walking will improve time in range on continuous glucose monitoring, as well as maternal and neonatal outcomes in pregnant patients with Type 2 diabetes. As an initial step in testing this hypothesis, we will conduct a randomized controlled trial to limit bias in evaluating these hypotheses. A FitBit will be provided to both groups to assess adherence to the walking regimen.

Each year, approximately 400 pregnant women with Type 2 diabetes are followed at Eastern Virginia Medical School Maternal Fetal Medicine. This would be the first randomized-controlled trial focusing on post-prandial walking utilizing continuous glucose monitoring and FitBit data in this US patient population.

2. Specific aims:

Aim 1. To examine the effect of post-prandial walking on time in range on CGM in pregnant patients with Type 2 diabetes

3. Study design:

We propose a randomized controlled trial of women with singleton pregnancies who present with a diagnosis of pre-gestational Type 2 diabetes. The participants will be randomized to the intervention group (post-prandial walks + standard care) or control group (standard care alone which includes the usual counseling regarding activity) in a 1:1 ratio. The participant will be randomized by a number-generating

computer software after recruitment at the gestational diabetes education class. All participants will receive a continuous glucose monitor and basic model FitBit for use and data collection.

Inclusion criteria

- Singleton gestation
- Known diagnosis of Type 2 diabetes OR meets new diagnosis of Type 2 diabetes in the first trimester (up through 13 weeks and 6 days)⁹

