Subjects will be screened and offered recruitment if they meet inclusion and exclusion criteria. This will occur at the EVMS Maternal Fetal Medicine Diabetes Program Clinic. The length of active participation will be variable depending on when they enter our care, and our intervention will continue throughout pregnancy. Our primary outcome length will last 2 weeks, but from randomization to postpartum, it can be up to 37 weeks (almost the entire pregnancy). No direct involvement is needed from the patient after delivery. However, data collection for secondary outcomes via chart review will continue to be collected through 2 weeks postpartum.

4.2 Consenting process:

Patients will be approached at the EVMS Maternal Fetal Medicine Diabetes Program. The patients will be informed that the purpose of the study is to evaluate the effect of physical activity on glucose control and that all participants will receive a FitBit Inspire 3 and continuous glucose monitor (Dexcom G7). The patients will be informed that the groups will receive two different types of counseling regarding physical activity. A patient may be withdrawn from the study if a provider outside of the research team no longer deems that participation is in the best interest of the patient. Participation in this research study will not affect any other aspect of the patient's care. The patient may withdraw from the study at any point without affecting her care. No inducements will be offered to terminate a pregnancy. Those engaged in this study will not take any part in decisions regarding termination of pregnancy and if the patient desires termination or questions the viability of the pregnancy, the patient will be referred to a non-investigator for appropriate care.

Due to the risk of introducing bias when divulging the details of the intervention group procedures to the control group, authorized deception will be utilized during the consent process. A general overview of the study that focuses on standard of care will be provided to the patients initially. If the patient is randomized to the intervention group, they will be provided with a second consent form outlining the randomization to 20 minute postprandial walks. Two separate consent forms will therefore be used: one for all participants prior to randomization, and another for the intervention group only outlining the specifics of the postprandial walk intervention.

5. Randomization:

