This will be a randomized-controlled trial 1:1. Randomization to each group will be conducted via the REDCap randomization module.

6. Outcomes:

Our primary outcome is the time in range (via CGM data) during the management of Type 2 diabetes in pregnancy between 34 and 36 weeks gestation. We chose this primary outcome because it is at the time of peak insulin resistance and time in range is more closely associated with pregnancy outcomes as compared to other means of monitoring glucose control.

Secondary outcomes include FitBit data (duration of postprandial walk (in minutes), sleep duration, baseline heart rate, maximal heart rate during walks, frequency of aerobic exercise per week), CGM data (mean glucose level, glucose excursions, fasting blood sugar), total daily insulin dose, fetal demise, fetal growth restriction, preeclampsia, placental abruption, mode of delivery (cesarean or vaginal delivery), indication of cesarean delivery, presence of shoulder dystocia (for vaginal deliveries), quantitative blood loss (QBL mL), postpartum hemorrhage (QBL > 1000 mL), infection (either chorioamnionitis or postpartum endometritis prior to discharge), birth weight (gram), APGAR scores, neonatal infection (defined as sepsis, fever, positive cultures, or a suspicious clinical course that warranted antibiotics treatment), respiratory distress syndrome, necrotizing enterocolitis, and neonatal intensive care unit admission (NICU), and days in NICU. Other secondary outcomes will include metabolomic markers collected from the urine and blood, as well as body composition data.

We will also collect demographic and clinical characteristics including maternal age, gestational age at delivery, race, ethnicity, insurance, marital status, history of preterm birth, parity, and number of previous cesarean or vaginal delivery.

Chart review for secondary outcomes and demographic/clinical characteristics will be completed through Allscripts, EPIC, and Powerchart.

7. Data Gathering and Safety:

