The FitBits, continuous glucose monitors, and all supplies for the patient will be paid for with no cost to the patient or the patient's insurance company. The [name] Discretionary Research Fund is covering the cost of the FitBits and CGMs. For the Dexcom G7, it is recommended that the sensor be changed every 7 days, which will be performed by the patient. Therefore, the sensor will need to be changed between 8 and 37 times throughout the study period, dependent upon what gestational age the patient was enrolled.

The research team will gather the data from the continuous glucose monitors via the share function, similar to how the data is shared to the clinical team.

The primary outcome will focus on the 34 through 36 week gestation data. However, the data from the rest of the subject's participation will be included in the secondary outcomes.

There will be two blood draws: at enrollment and again between 34 and 36 weeks gestation. A urine collection will also be performed at these times. These will be collected at an already scheduled clinic appointment.

Therefore, no additional appointment will be needed for this. It will be drawn by phlebotomy staff or research nurses. It will be kept refrigerated, processed within 24 hours, and kept in -70 degree freezer in a secured area. After collection, samples will be run and kept in a separate repository for potential future use. This will be paid by the [name] Discretionary Research Fund. There will be no cost to the patient.

The study dataset and ID key will be stored in REDCap in separate projects due to inclusion of data from the EMR.

8. Sample size calculation: Time in range in pregnant patients with pre-gestational diabetes is 66.3% with a standard deviation of 21.3% ³. We assume that 20 minutes of postprandial walking after each meal will decrease the mean glucose by 30%. Therefore, assuming a 30% improvement in time in range, with a power of 80% and alpha of 0.05, 18 mother/neonate pairs per group would be needed to reach statistical significance. Assuming a 10% loss to follow up rate, a total of 40 mother/neonate pairs will be included in the study.

9. Statistical analysis: Descriptive statistics will be provided first for describing the subjects' demographic and clinical characteristics. Fisher's exact or Chi Squared test will be used to compare categorical variables and the Student t-test or Man-Whitney U test will be used to compare numerical variables.

References:

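### Does the loose wording of the 34-to-36-week primary window leave the primary endpoint, or the sample size, open?

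*Protocol*

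**What the plan says.** The primary window appears in three places in the Protocol.

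- Section 6 (Outcomes), the endpoint definition: "time in range (via CGM data) during the management of Type 2 diabetes in pregnancy between 34 and 36 weeks gestation".
- Section 4.1 (Recruitment and Screening), the only stated length: "Our primary outcome length will last 2 weeks".
- Section 7 (Data Gathering and Safety), describing which sensor data are used: "The primary outcome will focus on the 34 through 36 week gestation data".

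Entry limits are given in weeks and days, for example "up through 13 weeks and 6 days" for a new diagnosis (section 3). The primary window is not.

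On pregnancies that may end before the window, section 1 lists the harms that better glucose control may reduce, "which include miscarriage, congenital birth defects, macrosomia, intrauterine fetal demise, and neonatal morbidity". Section 4.1 says of participation that "from randomization to postpartum, it can be up to 37 weeks". Section 7 expects that "the sensor will need to be changed between 8 and 37 times throughout the study period", depending on gestational age at enrolment. Section 8 needs 18 per group and reaches 40 in total: "Assuming a 10% loss to follow up rate".

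**The concern.** There are two worries.

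The first is the length of the window. If week 36 counts in full, the primary value averages 21 days, half as much again as the stated 2 weeks. In a trial of 40 women, the days that make up the primary value should not be open to choice once the data are in.

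The second is whether the value exists. Women enter before 32 weeks 0 days, some of them very early. A pregnancy that ends before 34 weeks has no time in range in the window. The sensor count seems to take participation to about term, since 32 weeks plus 8 changes at 7 days is 40 weeks. The 10% allowance is used in full by the step from 36 to 40 women. If early endings came on top of ordinary withdrawals, power would fall below its target.

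**Working it through.** **Reading the window.** 34w0d to 35w6d is 14 days; 34w0d to 36w6d is 21 days. Set side by side:

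- Section 4.1 states 2 weeks. This is the only length given.
- Section 6, the definition, agrees with 2 weeks.
- Section 7 alone allows 21 days. Its sentence separates the primary data from the data of the rest of participation; it does not define the endpoint.
- The inclusive use of the same preposition in section 3 does not show that week 36 runs to its sixth day, because there it ends at a named day. Section 4.1 also runs chart review to a point 2 weeks after delivery, and nobody would read that as 2 weeks and 6 days.

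**The plan's sample size.** Inputs from section 8: mean 66.3, SD 21.3, 30% improvement, power 80%, alpha 0.05 (two-sided reproduces the figure).

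- Difference: 0.30 × 66.3 = 19.89 points.
- n per group = 2 × (21.3 × (1.960 + 0.842) / 19.89)² = 18.00, the stated 18.
- Total: 36 / 0.90 = 40.0, the stated 40.
- Power at 18 per group: 80.0% by normal approximation, 77.7% by t-test. At 17 per group the t-test gives 75.2%.

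**What the choice of window does to the test.** Assume three weekly values with equal correlation r, and a 2-week mean with SD 21.3. The ratio of the 3-week to the 2-week SD, which is also the correlation between the two means, is √[2(1 + 2r) / (3(1 + r))].

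| r (assumed) | ratio | SD of 3-week mean | t-test power, 3-week | verdicts differ at the plan's effect |
|---|---|---|---|---|
| 0.9 | 0.991 | 21.1 | 78.4% | 3.3% |
| 0.7 | 0.970 | 20.7 | 80.1% | 6.1% |
| 0.5 | 0.943 | 20.1 | 82.3% | 8.6% |
| 0.3 | 0.906 | 19.3 | 85.2% | 11.4% |

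The last column comes from 100,000 simulated trials per row, 18 per group. With no effect, each reading on its own rejects in about 5% of trials. If someone took whichever reading was significant, the rate would be 5.7%, 6.2%, 6.6% and 7.0% in the same order.

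**Early-ending pregnancies.** The Protocol gives no rate of pregnancies ending before 34 weeks, so any figure is an assumption. With a further loss on top of the full 10%:

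| further loss (assumed) | evaluable women | t-test power |
|---|---|---|
| 0% | 36.0 | 77.7% |
| 5% | 40 × 0.90 × 0.95 = 34.2 | 75.4% |
| 10% | 40 × 0.90 × 0.90 = 32.4 | 73.0% |

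If early endings are already part of the 10%, the first row applies and nothing is lost.

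**The case for a change.** The strongest case for a change is that the inconsistency is on the page and is not just a detail left for later. Section 7 is where staff read which data feed the primary outcome, and it uses both forms, since the blood draws a few sentences on are placed between 34 and 36 weeks. An author of an analysis plan would inherit the conflict. The cost of settling it is a sentence or two. On early endings, the Protocol itself names events that end a pregnancy, yet its sensor count makes no mention of them.

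One part of this stands: the section 7 phrase is loose, and explicit day bounds would be better drafting. The rest does not carry a change.

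- The inflated error rate needs a choice between readings after the data are seen. Nothing in the Protocol permits one, and it states a length of 2 weeks.
- Differing verdicts in 3% to 11% of trials are what two closely correlated summaries of the same women produce. They do not show that either summary is wrong.
- The sensor count is an estimate of supplies. Section 4.1 says that participation varies and gives 37 weeks as a maximum, so the count is not a claim that every woman reaches the window.
- An allowance that is exactly used up is how attrition inflation works. Section 8 does not restrict the 10% to withdrawals.

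**Conclusion.** No change to the plan follows. The window has one stated length, 2 weeks, and the endpoint definition agrees with it; the section 7 phrase is a slip in wording that an analyst would resolve to 14 days. Had 21 days been meant, the test would still be valid at 5%, with power equal or slightly higher (about 78% to 85% against 77.7%). Those figures rest on assumed correlations and on the same treatment effect in each week.

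How pregnancies ending before or during the window enter the comparison is commonly set out in the statistical analysis plan, which is not shown, so its absence from the Protocol is not an error. The power cost of such losses cannot be fixed from the document, because it gives no rate and does not exclude them from the 10%. Neither the size nor the direction of any bias can be shown. Stating the 2-week window once in weeks and days would be good housekeeping, but it would alter no figure, rule or conclusion in the plan.

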- Age ≥ 18 and <50 years
- Gestational age <32 weeks 0 days gestation

Exclusion criteria

- Non-English as primary language.
- Inability to participate in 20 minutes of walking at a time
- Known or suspected fetal anomaly or aneuploidy
- Prisoners
- Management of diabetes outside of Eastern Virginia Medical School Maternal Fetal Medicine

Because we are a tertiary care center, some individuals may be seen at several different time points in the pregnancy at time of recruitment. All of these participants can be included for recruitment until 32 weeks 0 days gestation.

3.1 Postprandial walking:

Post-prandial walking group

Participants will be instructed to walk specifically for 20 minutes after each meal (breakfast, lunch, and dinner).

Control group

Participants will receive the usual counseling regarding physical activity, which does not include post-prandial walking.

Both groups

All participants will be encouraged to continue exercise per the U.S. Department of Health and Human Services Physical Activity Guidelines for Americans and the American College of Obstetricians and Gynecologists recommendations, which includes at least 150 minutes of moderate intensity aerobic activity per week during pregnancy. Given these recommendations, post-prandial walking is minimal risk to the patient and is an activity that patients may choose to do even outside of this study.

Both groups will have a fasting blood draw and urine sample at enrollment and between 34-36 weeks gestation in the outpatient setting, typically less than 25cc blood, to test for metabolomics.

Both groups will also have an estimation of body composition at enrollment and between 34-36 weeks gestation using bioelectrical impedance analysis (BIA), which introduces (non-invasively) a current into the body passing through a source electrode and a detector electrode, located on both hands and feet. BIA measures Resistance and Reactance and their vector relationship Impedance. Based on predictive equation, BIA estimates fat mass, fat-free mass, lean soft tissue, total body, intracellular, extracellular water, and phase angle. There are no known risks or discomforts related to the BIA. Minor discomfort is associated with the placement and removal of the electrodes on the skin.

4. Procedures:

4.1 Recruitment and Screening:

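### Does the FitBit outcome on post-meal walking fail because the protocol describes no record of meal times?

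*Protocol*

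**What the plan says.** Section 1 of the protocol states the device's purpose: "A FitBit will be provided to both groups to assess adherence to the walking regimen". Section 3.1 ties that regimen to meals for the walking arm: "Participants will be instructed to walk specifically for 20 minutes after each meal (breakfast, lunch, and dinner". Section 6 then lists the matching secondary outcome: "Secondary outcomes include FitBit data (duration of postprandial walk (in minutes), sleep duration". The same list has two related FitBit items, peak heart rate while walking and the weekly frequency of aerobic exercise.

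Under Both groups, Section 3.1 encourages every participant to reach "at least 150 minutes of moderate intensity aerobic activity per week during pregnancy". In arguing that the intervention carries minimal risk, it adds that post-meal walking "is an activity that patients may choose to do even outside of this study". Control counselling leaves post-meal walking out, and Section 4.2 withholds the regimen from controls: "authorized deception will be utilized during the consent process".

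For device data, Section 7 describes retrieval from the glucose monitor only. The protocol does not describe FitBit retrieval, a meal or walk diary, participant marking of walks, or a rule for which walks count as postprandial. Section 9 names general tests for numerical variables and does not say which variables will be compared between arms.

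**The concern.** Calling a walk postprandial takes two times, that of the walk and that of the meal. The FitBit can supply the first; nothing described supplies the second. Meanwhile the protocol itself encourages other activity in both arms, so recorded walking is not all regimen walking.

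The difficulty is greatest in controls. They have no assigned walks to tie a bout to a meal, so a control-arm value would have no clear meaning if the arms were compared on this variable. The protocol goes to some length to keep the regimen from controls, yet nothing described would show directly whether some of them walked after meals anyway. A later analysis plan could set a clock window but could not recover meal times that were never recorded.

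What is at stake is interpretation. If time in range did not differ between arms, readers would want to know whether the walks took place after meals and whether controls did the same.

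**Working it through.** **1. Does the primary analysis depend on this variable?** The inputs, from Section 8, are a mean time in range of 66.3%, an SD of 21.3%, a 30% improvement, 80% power and alpha 0.05 (two-sided assumed).

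- Difference, read as relative: 0.30 × 66.3 = 19.89 points.
- n per group = 2 × (1.960 + 0.842)² × 21.3² / 19.89² ≈ 18.0. Power at 18 per group is 0.79995 by the normal approximation. Strict rounding up gives 19, as does the t-based figure of 19.01, so the stated 18 is reproduced to within one.
- With 10% loss: 36 / 0.90 = 40, as stated.

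No FitBit quantity enters. The primary outcome is read from the glucose monitor over a window that Section 4.1 describes thus: "Our primary outcome length will last 2 weeks".

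**2. How much walking is assigned?** From Section 3.1:

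- 3 walks × 20 min × 7 days = 420 min/week (60 min/day).
- Over the two-week window: 3 × 14 = 42 walks, or 42 × 20 = 840 min per woman in the walking arm.

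**3. Can the misclassification be bounded from the protocol?** Suppose other walking is exactly 150 min/week. A walking-arm woman recorded at 420 min/week then has at least 420 − 150 = 270 min after meals (270/420 = 64% adherence). A control recorded at 150 min/week has between 0 and 150 (0 to 150/420 = 36% of the regimen).

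These are illustrations, not bounds. The guideline figure is a minimum. If other walking is x min/week, the post-meal part of 420 recorded minutes is at least max(0, 420 − x), and this reaches 0 once x = 420. The control range simply restates the assumed total. Both ranges also treat the FitBit as a weekly counter and ignore the times of the bouts. The documents therefore give no figure for the size of the error.

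**4. What can still be measured?** Assume 150 min/week of guideline activity in both arms, all done as walking, with full adherence and no contamination:

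| Case | Walking arm | Control arm | Difference per week | Difference per day |
|---|---|---|---|---|
| Walks added to guideline activity | 570 min | 150 min | 420 min | 60 min |
| Walks replace guideline activity | 420 min | 150 min | 270 min | 38.6 min |

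Total walking is defined for every participant and needs no meal times. In the walking arm, three daily bouts of about 20 minutes form a recognisable pattern in time-stamped data. The weekly frequency of aerobic exercise, already listed in Section 6, also applies to both arms.

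**5. Would a change help?** Renaming the outcome as total walking alters the label without adding information, and it drops the only listed measure specific to the intervention. The other route is a meal log. Entry requires "Gestational age <32 weeks 0 days gestation", so a one-week log in week 33 would reach everyone before the primary window, at 3 × 7 = 21 entries each. But it could draw controls' attention to meals and activity just before the primary outcome is measured, and it would record nothing meal-linked within the 34 to 36 week window.

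**The case for a change.** The strongest case for a change is that data capture belongs in the protocol. An analysis plan can choose a window or a bout rule but cannot create meal times. Glucose rises on the monitor might stand in for meals, but the protocol does not propose this, and meal times inferred that way would be tied to the very glucose outcomes under study. Peak heart rate during walks has the same weakness. A cheap fix is also at hand: one sentence saying how a post-meal walk is identified, with that variable kept for walking-arm adherence and total activity used to compare the arms.

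Much of this stands. Meal-linked walking will be measured imprecisely, and meal-linked contamination in controls will not be measured directly. It does not follow that nothing can be measured. The protocol says nothing at all about FitBit data handling, so whether participants start and stop recordings is unknown; this is an operational omission, not a contradiction. The harm also depends on a between-arm test of this variable, which Section 9 does not specify. The remark about patients choosing such walks themselves supports a statement about risk and is weak evidence that contamination is expected. The suggested sentence describes what a competent analyst would do anyway on seeing the data.

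**Conclusion.** No change to the plan follows. The protocol lists a post-meal walking duration without saying how a walk is identified as postprandial, and that is a real gap in detail. It concerns one process measure in a long secondary list. The primary outcome, the 18 per group, the total of 40 and the main comparison do not depend on it.

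Analysts can fill the gap sensibly by reporting time-stamped walking bouts as approximate adherence in the walking arm and showing separation between arms on an activity measure defined for everyone. With full adherence and no contamination, that separation would be 270 to 420 min/week. This assumes that both arms take up the 150 min/week of guideline activity as walking, and that the device's time-stamped activity data are retrieved, which the protocol does not describe. Meal-specific adherence would remain approximate, and reports should word it that way. A meal log is a debatable trade-off in a trial that withholds the regimen from controls, and renaming the outcome brings no clear gain.

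### Maximal walking heart rate is listed as a trial outcome without limit to one arm, but only one arm is prescribed walks, so a test between arms would not be a randomised comparison

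*Protocol*

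**What the plan says.** Section 6 opens its list with "Secondary outcomes include FitBit data (duration of postprandial walk (in minutes), sleep duration, baseline heart rate" and continues with "maximal heart rate during walks, frequency of aerobic exercise per week". Nothing there limits the walk-based items to one arm. The same sentence does restrict another conditional outcome: shoulder dystocia is to be recorded for vaginal births only.

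Section 3.1 gives the arms different instructions. For the walking arm: "Participants will be instructed to walk specifically for 20 minutes after each meal (breakfast, lunch, and dinner". For controls: "Participants will receive the usual counseling regarding physical activity, which does not include post-prandial walking". Both arms are encouraged to do "at least 150 minutes of moderate intensity aerobic activity per week during pregnancy", and the same section accepts that patients may take such walks outside the study. Under Section 4.2 the walking details are disclosed only to women allocated to walk.

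Section 9 states that "the Student t-test or Man-Whitney U test will be used to compare numerical variables", with no exception for walk-based measures. The Background (Section 1) gives the purpose of the device: "A FitBit will be provided to both groups to assess adherence to the walking regimen". Section 4.1 says of the main window: "Our primary outcome length will last 2 weeks". Section 7 adds data from outside the 34 to 36 week window to the secondary outcomes.

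**The concern.** The measure exists only for a woman who walks. Walking is prescribed in one arm and left to choice in the other, so having a value at all depends on allocation and on behaviour after it. Followed as written, Sections 6 and 9 compare the women in the walking arm who walk, most of them because they were told to, with those controls who walk by choice. Randomisation does not protect that contrast. Control walkers may be fitter, less fit or more motivated than controls who do not walk, and the bias can go either way.

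The wording also leaves open a single maximum over all of a woman's walks. Such a maximum depends on how many walks it is taken over, and the number of walks is what the intervention changes. A higher value in the walking arm could then be read as harder exertion per walk when the average walk is no harder. In a trial whose Section 3.1 describes the walking as minimal risk, a misleading exertion result in either direction is worth avoiding, although it is one of many secondary outcomes.

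**Working it through.** **1. Who has a value.** This step needs no arithmetic.

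| | Walking arm | Control arm |
|---|---|---|
| Walks prescribed | 3 a day, 20 minutes each | none |
| General activity advice | at least 150 minutes a week | at least 150 minutes a week |
| FitBit worn | yes | yes |
| Value exists if | she walks, as instructed | she chooses to walk |

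The analysed controls are therefore selected by something that happens after randomisation. This holds however the peaks are summarised, because a mean of per-walk peaks is also undefined for a woman with no walks.

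**2. How far a single maximum moves with the number of walks.** The protocol gives no figure for this outcome, so there is none to reproduce. The inputs are:

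- Walking arm, from Sections 3.1 and 4.1: 3 walks a day × 14 days = 42 at full adherence.
- Control arm, assumed: 5 walks in two weeks, or 15. The 15 comes from the activity advice if all of it were taken as 20-minute walks: 2 × 150 / 20 = 15.
- Walk-to-walk SD of a woman's peak heart rate, assumed: 8 bpm, range 6 to 10. The documents give none.
- Peaks are independent and normal, with the same distribution in both arms, so there is no true difference in intensity.

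For k walks the expected maximum, in SDs above the woman's own mean, is E(k) = ∫ x · k · φ(x) · Φ(x)^(k−1) dx. By numerical integration:

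| k | 5 | 15 | 21 | 30 | 42 |
|---|---|---|---|---|---|
| E(k) | 1.163 | 1.736 | 1.889 | 2.043 | 2.180 |

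The gap between arms is SD × [E(k walking) − E(k control)]:

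| Walks, walking arm vs control | Difference in E | SD 6 | SD 8 | SD 10 |
|---|---|---|---|---|
| 42 vs 5 | 1.017 | 6.1 | 8.1 | 10.2 |
| 42 vs 15 | 0.444 | 2.7 | 3.6 | 4.4 |
| 30 vs 15 | 0.307 | 1.8 | 2.5 | 3.1 |
| 21 vs 15 | 0.153 | 0.9 | 1.2 | 1.5 |

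(Gaps in bpm.) If every peak were identical, the SD and the gap would both be zero.

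**3. What a t-test would do with it.** Two arms of 18 (the per-group number in Section 8) were simulated 4,000 times with identical per-walk distributions and an assumed between-woman SD of 10 bpm. Every control was given a value, so this isolates the count effect from the selection in step 1. False-positive rate at the 5% level, using one maximum per woman:

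| Walks | SD 5 | SD 8 | SD 10 |
|---|---|---|---|
| 42 vs 6 | 25% | 49% | 64% |
| 42 vs 14 | 10% | 17% | 24% |
| 42 vs 42 | 5% | 5% | 4% |

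When each woman's mean of per-walk peaks replaces the maximum, the rate stays near 5% in every scenario.

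**The case against.** The best reply is that the count effect rests on a definition the protocol does not contain. Section 6 does not say whether the peak is taken once over all walks or per walk and then averaged, and an average of per-walk peaks does not grow with the number of walks. Such summary rules commonly sit in an analysis plan, which is not at hand here. This stands: the count effect can only be stated conditionally, and the missing rule is not itself a finding.

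The size can also be challenged. Five control walks and full adherence to 42 are favourable choices when both arms receive the same general activity advice. This stands too. With 15 control walks and SD 8 the gap falls from 8.1 to 3.6 bpm, and with 21 walks against 15 it is 1.2 bpm.

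If allocation leads to more walks and more walks lead to a higher maximum, that difference is an effect of allocation. This is correct. The count effect misleads only when the result is read as intensity per walk. The selection of control walkers is a separate problem and is not answered by this.

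Finally, Section 9 is generic and the FitBit is there for adherence, so description in the walking arm may be what the sponsor intends. That may be so, but the measure is listed as an outcome without restriction, Section 9 makes no exception, and the restriction on shoulder dystocia shows that the authors limit conditional outcomes when they mean to.

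**Conclusion.** The point holds as a minor one. As written, maximal walking heart rate is an outcome conditional on walking, in a trial where one arm is prescribed walks and the other is not. A two-sample test of it compares the walking arm with a self-selected subset of controls. That conclusion rests on Sections 3.1, 6 and 9 alone and needs no assumption about heart rates.

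The inflation with walk count applies only if a single maximum over all walks is used and peaks vary from walk to walk. On the assumed SDs of 6 to 10 bpm and full adherence over two weeks, it is about 6 to 10 bpm against 5 control walks and about 3 to 4 bpm against 15, and less with lower adherence.

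A reader might infer two stronger things. One is that no control has a value; Section 3.1 does not support this, since controls are encouraged to be active and some will walk. The other is that the protocol has built in a false difference of about 8 bpm; it has not, because it fixes neither the summary rule nor the control walk count.

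Time in range, the sample size and the clinical outcomes are untouched.

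**What to change.** In Section 6, mark maximal walking heart rate as descriptive and reported in the walking arm only, defined as each woman's mean of her per-walk peak heart rates, to show the intensity delivered alongside adherence. In Section 9, exclude it from the between-arm tests. For a heart-rate comparison between arms, keep the baseline heart rate that Section 6 already lists; it does not depend on walking, and both arms wear the device. No new outcome is needed.

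The cost is a sentence or two of wording. The same FitBit data are used, with no further visits or participants.
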